aPTT	Activated Partial Thromboplastin Time
APOC	African Program for Onchocerciasis Control
AST	Aspartate Aminotransferase
AV	Atrioventricular
AUC	Area Under the Curve
BID	Bis indie (twice-daily)
BMI	Body Mass Index
BP	Blood pressure
Bw	Body weight
¹⁴ C	Carbon-14
CBC	Complete Blood Count
CI	Confidence Interval
CIOMS	Council for International Organizations of Medical Sciences
CK	Creatinine Kinase
CL	Clearance
C _{max}	Maximum concentration
C _{min}	Minimum concentration
CNS	Central Nervous System
CRF	Case Report Form
CRO	Contract Research Organization
CV	Coefficient of Variation
CYP3A4	Cytochrome P450 3A4
DALY	Disability-Adjusted Life Years
DNDi	Drugs for Neglected Diseases initiative
ECG	Electrocardiogram
EMA	European Medicines Agency
F	Female
F (parameter)	Bioavailability
FDA	Food and Drug Administration
FIH	First-In-Human
GABA	Gamma-Aminobutyric Acid
GCP	Good Clinical Practice
GDRC	Generic Document Review Committee
GGT	Gamma-Glutamyl Transpeptidase
GI	Gastro Intestinal
GLDH	Glutamate Dehydrogenase
GLP	Good Laboratory Practice
GMP	Good Manufacturing Practice

GP	General Practitioner
HDL	High Density Lipoprotein
hERG	Human ether-a-go-go-related gene
HbA1c	Glycated Haemoglobin A1c
HIV	Human Immunodeficiency Virus
HMR	Hammersmith Medicines Research
HR	Heart Rate
IR	Immediate Release
IC20	Inhibitory Concentration 20
ICF	Information Consent Form
ICH	International Conferences on Harmonization
IMP	Investigational Medicinal Product
IRB	Institutional Review Board
IV	Intravenous
LDH	Low Density Lipoprotein
LF	Lymphatic filariasis
LFTs	Liver function tests
LSF	Liquid Service Formulation
M	Male
MCV	Mean Corpuscular Volume
MCH	Mean Corpuscular Haemoglobin
MCHC	Mean Corpuscular Haemoglobin Concentration
MDA	Mass Drug Administration
MedDRA	Medical Dictionary For Regulatory Activities
Mg	Milligram
MIC	Minimum Inhibitory Concentration
MIC ₁₀₀	Minimum Concentration for 100% Inhibition
mL	Millilitre
MRT	Mean Residence Time
MTT	4,5-Dimethylthiazol-2-Yl)-2,5-Diphenyltetrazolium Bromide
NOAEL	No Observed Adverse Effect Level
NOEL	No Observed Effect Level
Ng	Nanogram
OCP	Onchocerciasis Control Program
OD	Omnie die (once-daily)
OGTT	Oral Glucose Tolerance Test
PD	Pharmacodynamic
P-gp	P-glycoprotein
PI	Principal Investigator (See Note Section 13)
PK	Pharmacokinetics
p.o	Per Os (To Be Taken By Mouth)
Ppm	Parts Per Million
PR	PR Interval
PT	Prothrombin Time

PTT	Partial Thromboplastin Time
RBC	Red Blood Cell
REC	Research Ethics Committee
QRS	QRS Interval
QTcB	Qtc Corrected By Bazett's Formula
QTcF	Qtc Correct By Fridericia's Formula
SAD	Single-Ascending Dose
SAE	Serious Adverse Event
SAS	Statistical Analysis System
SAR	Serious Adverse Drug Reaction
SD	Standard Deviation
SOC	System Organ Class
SRG	Safety Review Group
SST	Serum-Separating Tube
SUSAR	Serious Unexpected Adverse Event
$t_{1/2}$	Half-life
TEAE	Treatment-Emergent Adverse Event
T_{max}	Time Of At Which C_{max} Is Observed
TSH	Thyroid-Stimulating Hormone
ULN	Upper Limit Of Normal
UV	Ultraviolet
V_z	Volume of Distribution
WBC	White Blood Cell
WHO	World Health Organization
WNL	Within Normal Limits

PROTOCOL SUMMARY

Trial Objectives
	
Primary Objective:
 
 To investigate the safety and tolerability of emodepside (BAY44-4400) after multiple doses, administered as a Liquid Service Formulation (LSF) oral solution, in healthy male Caucasian subjects 
Secondary Objectives:
 
 To investigate the pharmacokinetics (PK) of emodepside (BAY44-4400) after multiple doses, administered as an LSF oral solution. To investigate the time-matched profiles of selected pharmacodynamics (PD) markers in plasma after multiple doses of emodepside (BAY44-4400), administered as an LSF oral solution.

Trial Endpoints
	
Safety and Tolerability Variables:
 
 Adverse events (AEs) Physical and neurological examination findings (including assessments of tremor of the hands and fingers, coordination/cerebellar function (finger to finger, finger to nose, with eyes open and closed), pupil size and reaction to light) Vital signs: heart rate (HR), systolic and diastolic blood pressure (BP) 12-lead Electrocardiogram (ECG (including HR, PR, QRS, QTcB, QTcF)) Clinical laboratory tests: 
Haematology: haemoglobin, haematocrit, mean corpuscular volume (MCV), mean corpuscular haemoglobin (MCH), mean corpuscular haemoglobin concentration (MCHC), platelets, reticulocytes, white blood cells (WBC) including differential, red blood cells (RBC), glycated haemoglobin (HbA1C) (at screening and Day 120 only);
 
Coagulation: activated partial thromboplastin time (aPTT), prothrombin time (PT);
 
Biochemistry: serum aspartate aminotransferase (AST), alanine aminotransferase (ALT), alkaline phosphatase (AP), glutamate dehydrogenase (GLDH), gamma-glutamyl transpeptidase (GGT), lactate dehydrogenase (LDH), creatine kinase (CK), amylase, lipase, free T3 and T4, thyroid-stimulating hormone (TSH), glucose, cholesterol (HDL, LDL, total), triglycerides, creatinine, urea, uric acid, bilirubin (total and conjugated), total protein, sodium, potassium, calcium, chloride, and magnesium;
 
At baseline (screening visit 1) and day 9 additional hormones: leptin and prolactin levels
 
Urinalysis: by dipstick – glucose, ketone bodies, specific gravity, occult blood, pH, proteins, leucocytes, bilirubin, urobilinogen, nitrites.
 
 Ophthalmology assessments, including visual symptoms, past ocular history, best corrected distance visual acuity, colour vision assessment, Amsler grid assessment

	
Pharmacodynamic Variables:
 
 • Time-matched profiles of glucose, glucagon, insulin, and cortisol. • Oral glucose tolerance test (OGTT) 
Pharmacokinetic Variables:
 
Emodepside plasma concentration–time data will be used to derive the following PK parameters of emodepside:
 
 • After the first dose of emodepside (Day 0): • Main PK parameters: 
 • Cohorts 1 & 2: AUC_{24}, AUC_{24}/D, C_{max}, C_{max}/D • Cohort 3: AUC_{12}, AUC_{12}/D, C_{max}, C_{max}/D • Exploratory PK parameters: 
 • Cohorts 1 & 2: $AUC_{24,norm}$, $C_{max,norm}$, t_{max}, MRT_{last}, V_z/F • Cohort 3: $AUC_{12,norm}$, $C_{max,norm}$, t_{max}, MRT_{last}, V_z/F • After multiple doses of emodepside (Day 9): • Main PK parameters: 
 • Cohorts 1 & 2: AUC_{∞}, AUC_{∞}/D, AUC_{24}, AUC_{24}/D, $C_{max,ss}$, $C_{max,ss}/D$ • Cohort 3: AUC_{∞}, AUC_{∞}/D, AUC_{12}, AUC_{12}/D, $C_{max,ss}$, $C_{max,ss}/D$ • Exploratory PK parameters: $AUC_{\infty,norm}$, $AUC_{12,norm}$, $AUC_{24,norm}$, AUC_{last}, AUC_{last}/D, $AUC_{last,norm}$, $C_{max,ss,norm}$, $t_{1/2}$, λ_z, t_{max}, MRT_{∞}, V_z/F, CL_{ss}/F • Other optional parameters: AUC_{t-inf}, $\%AUC_{extra}$, points terminal • Accumulation ratios $RA(C_{max})$ and $RA(AUC_{\tau})$ will be calculated • C_{trough} will be derived from the concentration data (Days 1–9). 
The above parameters may be calculated for the metabolites of emodepside, as appropriate.
 
In urine, the amount and concentration of emodepside and its metabolites may be measured for up to 24 h on up to 4 occasions during the study. The appropriate specific PK parameters to be calculated will be decided, according to the concentration.


Trial Design
	
This will be a single-centre, single-blind, randomized, placebo-controlled, parallel-group, multiple-dose, dose-escalation study.
 
The study will evaluate safety, tolerability, PK and PD of emodepside, after administration as an LSF oral solution, over 10 days, in healthy male Caucasian subjects. Treatment duration was defined based on single ascending dose PK data modelling as well as anticipated duration of treatment with emodepside for safety.
 
The study will be performed in a single site specialized in Phase 1 studies.
 
Each cohort will comprise 8 healthy Caucasian male subjects, 6 of whom will be allocated to receive emodepside, and 2 of whom will be allocated to receive placebo. 3 cohorts will be recruited, to test 3 multiple dose levels of

	
emodepside LSF oral solution.
 
This will be a single-blind study. The Investigator and Sponsor will remain blinded, so as not to potentially introduce bias. However, the Investigator and Sponsor may choose to review unblinded data at the Safety Review Group for a particular cohort (the process will be described in the Safety Review Group Charter).
 
Each subject will attend a screening visit within the 4 weeks before their first dose of study medication (on Day 0).
 
Eligible subjects will be admitted to the ward on the evening of Day -3. They will remain on the ward until the morning of day 14 (17 nights in a row), during which they'll receive once- or twice-daily oral doses of emodepside or placebo for 10 days. Safety, tolerability, PD and PK assessments will be done regularly before, during, and after dosing. Each subject will undergo a full day of assessments (excluding PK) on the day before dosing (Day -1), and a similar full day of assessments (including PK) on the first (Day 0) and last days of dosing (Day 9). In addition, they will undergo an Oral Glucose Tolerance Test (OGTT) on Day -2, Day 1, Day 8 and Day 120.
 
Subjects will be discharged from the ward 5 days after their last dose of study medication, if the Investigator has no safety concerns. Subjects will attend the ward for out-patient visits on Days 17, 20, 23 and 27 (+/- 2 days). Subjects will attend a follow-up visit on Day 30 (+/- 2 days), and 3 long-term follow-up visits on Days 60, 90 and 120 (+/- 2 days).
 
The end of the trial is defined as the final long-term follow-up visit by the last subject (or final contact with the subject if that is later). If the trial is terminated early, the trial ends when the Sponsor notifies the Investigator in writing that the trial has finished, or when the last subject attends the final long-term follow-up visit, whichever is later.


Main Entry Criteria
	
Inclusion:
 
 1. Male, Caucasian volunteers, deemed healthy based on a clinical history, physical examination, ECG, vital signs, and laboratory tests of blood and urine. 2. 18 to 45 years of age. 3. Normal body weight (BMI; Quetelet index) in the range 18 to 30.1 kg/m² at screening. 4. Blood pressure and heart rate in the supine position prior to randomisation must be within the ranges 
 • 90–140 mm Hg systolic, • 60–90 mm Hg diastolic; • heart rate 45-100 beats/min. 5. Sufficient intelligence to understand the nature of the trial and any hazards of participating in it. Ability to communicate satisfactorily with the Investigator and to participate in, and comply with the requirements of, the entire trial. 6. Willingness to give written consent to participate, after reading the information and consent form, and after having the opportunity to

discuss the trial with the Investigator or his delegate.

7. Willingness to agree to the contraceptive requirements of the study from the first dose until 120 days after the last dose of study medication
8. Willingness to give written consent to have data entered into the Overvolunteering Prevention System

Exclusion:

9. Administration of a licensed or unlicensed medicinal product as part of another clinical trial within the 3 months before, or within 5 half-lives of, their first dose of study medication, whichever is longer, or is currently in the follow-up period for any clinical trial.
10. Clinically relevant abnormal medical history, concurrent medical condition, acute or chronic illness or history of chronic illness (such as diabetes mellitus or other abnormalities of glucose homeostasis) sufficient to invalidate the subject's participation in the trial or make it unnecessarily hazardous.
11. Past surgery (eg stomach bypass) or medical condition that might affect absorption of study drug taken orally.
12. Presence of abnormal physical findings, ECG, or laboratory values at the pre-trial screening assessment that could interfere with the objectives of the trial or the safety of the subject.
13. Loss of more than 400 mL of blood within 3 months before admission.
14. Clinically relevant history of vital organ disease or other disease of an organ or the central nervous system.
15. Current or previous medical or psychiatric disorder, condition or history of such (eg seizures) that, in the opinion of the Investigator or the Sponsor, would increase the risk associated with study participation, or impair the subject's ability to participate or complete this study.
16. Positive test for hepatitis B, hepatitis C or HIV
17. Febrile illness within 1 week before the first dose of study medication.
18. History of severe allergy, non-allergic drug reactions, severe adverse reaction to any drug, or multiple drug allergies.
19. Subjects with hypersensitivity to any ingredient of the study medication, including the active ingredient, emodepside.
20. Presence or history of drug or alcohol abuse in the last 10 years, or intake of more than 21 units of alcohol weekly.
21. Regular daily consumption of more than one liter of xanthine-containing beverages.
22. Regular daily consumption of more than 5 cigarettes daily, or use more than 3 grams (1/8 ounce) of tobacco.
23. Use of a prescription medicine during the 28 days before the first dose of study medication or use of an over-the-counter medicine (with exception of acetaminophen (paracetamol)), during the 7 days before the first dose of study medication.
24. Use of dietary supplements or herbal remedies (such as St John's

	
Wort) that are known to be inducers or inhibitors of CYP3A4, or other co-medications known to be relevant substrates of CYP3A4, during the 28 days before the first dose of study medication (see list in the Study Procedures Manual).
 
25. Use of dietary supplements or herbal remedies (such as St John's Wort) that are known to be strong inhibitors of P-gp, or other co-medications known to be relevant substrates of P-gp, during the 28 days before the first dose of study medication (see list in the Study Procedures Manual).
 
26. Relevant pathological abnormalities in the ECG at screening, such as a second or third-degree AV block or prolongation of the QRS complex over 120 msec or QTc-interval over 450 msec (QTcB or QTcF).
 
27. Evidence of drug abuse (via urine testing) at the screening assessment or admission to the ward
 
28. Use of excluded therapies that may impact on the interpretation of study results in the opinion of the Investigator or Sponsor.
 
29. Objection by General Practitioner (GP) to subject entering trial.
 
30. History of residing for 6 or more continuous months, within the last 3 years, in regions with endemic parasitic infections as determined by the Investigator.
 
31. Possibility that subject will not cooperate with the requirements of the protocol.
 
32. No contact lenses wear within 1 month before dosing. Contact lenses wear is not permitted during the study.
 
33. Any ocular disorder for which topical ocular therapy is currently or chronically prescribed, including inflammatory eye disease (dry eye allergic conjunctivitis [seasonal allergic conjunctivitis, vernal keratoconjunctivitis, atopic keratoconjunctivitis], uveitis and glaucoma)
 
34. Past history of ocular disease requiring ongoing treatment
 
35. Past ocular surgery including laser or other refractive corneal surgery
 
36. Evidence of eye irritation, visual difficulties, corneal opacity, ocular surface (corneal or conjunctival damage, with or without ocular symptoms)
 
37. Evidence of narrow anterior chamber angles causing increased risk of acute glaucoma
 
38. Evidence of ocular media opacity including lens opacity/vitreous opacities
 
39. Evidence of retinal or optic nerve pathology
 
40. Evidence of pronounced colour blindness, as indicated by an Ishihara score of 9/13 or below


Removal of subjects from study
	
 • Subjects may withdraw from the study at any time at their own request, or they may be withdrawn at any time at the discretion of the Investigator or Sponsor for safety, behavioural, or administrative reasons. • Subjects who withdraw, or are withdrawn from the study may be replaced

	at the discretion of the Investigator upon consultation with the Sponsor.												
Study Duration	
 Each subject's participation in the study will last for up to 21 weeks, and will include a screening visit (within 4 weeks before dosing), an in-house 2-week evaluation period (Day -3 to Day 14), followed by 4 outpatient visits (on Days 17, 20, 23 and 27), a follow-up visit (on Day 30), and 3 long-term follow-up visits (on Days 60, 90 and 120). 												
Study treatments	
Test-Drug: Emodepside LSF oral solution (1 mg/mL) or matching placebo. Planned dose levels:
 
  
 Cohort	Dose level	Formulation	
   
 1	5 mg, OD, for 10 days	LSF oral solution (1 mg/mL)	
 
 2	10 mg, OD, for 10 days	LSF oral solution (1 mg/mL)	
 
 3	10 mg, BID, for 10 days (single dose on Day 9)	LSF oral solution (1 mg/mL)	
  
 
Emodepside administration will be given as fasted doses of LSF oral solution. Each morning dose will be given after an overnight fast of at least 9 h. On Days 0, 1, 8 and 9, subjects will fast until at least 4 h after dosing. On Days 2 to 7, subjects will fast until at least 1h after dosing. In Cohort 3, subjects will also fast for 2 h before and until 1 h after their evening dose.
 
Dose escalation will be decided by the Safety Review Group (SRG) at the Safety Review Meeting. The dose will not be escalated until the SRG have reviewed safety, tolerability and PK data until 48 h after the final dose of study medication in at least 4 subjects on active treatment (ie, at least 6 subjects overall), and agree that it is appropriate to give a higher dose; that decision will be taken in the Safety Review Meeting, before dosing of the subsequent cohort. The next planned dose level may be reduced, or a dose level may be re-tested or an intermediate dose level selected, based on emerging data.
 
The dose level will not exceed 20 mg LSF oral solution (1 mg/mL) per day.
 
If, within a treatment group, any of the following occurs, dose escalation will be stopped:
 
Safety stopping criteria
 
 There is 1 or more SAE, considered to be related to emodepside; 2 or more subjects in the same treatment group who present any severe or clinically significant AEs considered to be related to emodepside 
If a cohort fulfils a dose escalation stopping criterion, that dose level will not be repeated.
 
PK stopping criteria
 
 predicted mean plasma concentrations in the subjects at the next scheduled dose level exceed or equal: C_{max} 612 µg/L (based on the highest dose in the Single Ascending Dose (SAD) study DNDi-EMO-001)) 
The scheduled dose of emodepside may be reduced if, for example, the results of safety tests give any cause for concern, or tolerability is poor.
	Cohort	Dose level	Formulation	1	5 mg, OD, for 10 days	LSF oral solution (1 mg/mL)	2	10 mg, OD, for 10 days	LSF oral solution (1 mg/mL)	3	10 mg, BID, for 10 days (single dose on Day 9)	LSF oral solution (1 mg/mL)
Cohort	Dose level	Formulation											
1	5 mg, OD, for 10 days	LSF oral solution (1 mg/mL)											
2	10 mg, OD, for 10 days	LSF oral solution (1 mg/mL)											
3	10 mg, BID, for 10 days (single dose on Day 9)	LSF oral solution (1 mg/mL)											

	
If AEs occur that cause mild or moderate discomfort but do not in any way threaten the health of the subject, that dose level may be repeated with the aim of exploring further the relationship between dose and AE. If, in the judgement of the Safety Review Group (SRG), it would not be reasonable to expose further subjects to the level of discomfort experienced by the subjects who have already received the dose, the next scheduled dose may be reduced. The reduction may be either to one of the dose levels that has already been given, or to an intermediate level that has not previously been given; in either case, the aim is to learn more about the relationship between AE and dose (or plasma concentration) of drug.

Sample Size
	
Up to 24 healthy male subjects (not including replacement subjects), in up to 3 cohorts, of 8 subjects.


Statistics
	
No formal statistical sample size estimation has been performed for this, due to the exploratory nature of this study.
 
6 subjects per dose level (cohort) is considered sufficient to examine the safety and tolerability of emodepside as well as the pharmacokinetics after single and multiple doses. Any withdrawn subjects will be replaced.
 
Interim analyses will be performed.
 
Safety:
 
Safety and tolerability data will be summarized using the Safety Population. Safety and tolerability data will be summarized using the following parameters:
 
 • Vital signs; • 12-lead ECG; • Haematology; • Clinical chemistry; • Coagulation; • Urinalysis; • Physical and neurological examination; • Ophthalmology assessments • AEs. 
No formal hypothesis testing of these parameters will be carried out.
 
Pharmacodynamic:
 
PD data will be summarized using the Safety Population. PD variables at each planned assessment, and change in PD variables from baseline at each planned post baseline assessment, will be summarised by actual treatment.
 
Pharmacokinetic:
 
PK concentration data will be summarised using the PK Concentration population. PK parameters will be summarised using the PK Parameter population.
 
For log-transformed parameters, the primary measure of central tendency will be the geometric mean; for untransformed parameters, it will be the arithmetic

	
mean or median.
 
For all variables, N (number of subjects in receiving the treatment/formulation in the population), n (number of observations), arithmetic mean, median, minimum, maximum, Standard Deviation (SD), % Coefficient of variance (%CV), and the 95% confidence interval of the arithmetic mean will be derived. For log transformed variables, all of the above plus the geometric mean, its 95% confidence interval, and the SD of the log-transformed variables, will be provided.
 
Plasma concentrations and PK parameters of emodepside and metabolites will be listed and summarised, by treatment, using descriptive statistics. Individual and mean plasma concentration–time profiles will be presented graphically.
 
Concentrations of emodepside and its metabolites in urine may be determined and the amount of emodepside excreted in the urine will be estimated, if applicable

--	--

1. Background and Study Rationale

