In fasting conditions, a dose and plasma concentration-dependent decrease in insulin plasma concentration (13 pmol/L or below) after emodepside administration was reported, with a maximum between 0 and 4 h. In parallel, dose and plasma concentration-dependent increases in fasting serum glucose levels above 5.8 mmol/L were observed, with a maximum between 0 and 4 h (none of these increases were considered clinically significant by the Investigator, and therefore were not reported as AE) and a maximum of 12.7 mmol/L at 2 h at the dose of 40 mg LSF solution. In fasted conditions, both blood insulin decrease and glucose increases occurred over the 4 h after single dosing with emodepside in most cases. In Cohort 9 (6 subjects exposed to emodepside, and 2 subjects to placebo), 10 mg LSF of emodepside was given with food and a physiological increase of glucose and insulin was observed, as expected under normal conditions. A decrease in insulin due to emodepside could not be observed. This is interpreted that administration of food overrules a possible effect of emodepside on the secretion of insulin under fasted condition.

There was no report of clinically significant laboratory abnormalities, or abnormalities in vital signs, ECG parameters or physical examination throughout the study, regardless of the formulation.

Data of Cohort 10 (treated with a single 40 mg dose of emodepside and focused at ocular system assessment) are still under analysis, however no serious AEs were reported following administration of the LSF of 40 mg. 6 subjects were exposed to emodepside, and, 2 subjects to placebo. Overall in cohort 10, 22 non-serious AEs related to emodepside were reported, all mild or moderate in severity. 4 subjects reported AEs related to emodepside (eye disorders including blurred vision, photopsia, visual impairment, eye pain and reduced visual acuity), with an onset in

most cases close to T_{max} and of various durations. In addition, the following were considered related to emodepside: 2 subjects reported concomitant feeling of relaxation, 1 subject reported dizziness, 1 subject reported disturbance in attention and hypervigilance, 1 subject reported concomitant balance disorder and disorientation, and 1 subject reported oral paresthesia (of the tongue) that lasted for approximately 6 h.

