7.5. Dose escalation

During the study, the dose will be increased only if the safety, tolerability and PK of the previous dose are acceptable.

Dose escalation will be decided by the Safety Review Group (SRG) at the Safety Review Meeting (see Section 11). The dose will not be escalated until the SRG have reviewed the safety, tolerability and PK data until 48 h after the final dose of study medication in at least 4 subjects on active treatment (ie. at least 6 subjects overall) and agree that it is appropriate to give a higher dose; that decision will be taken in the Safety Review Meeting, before dosing of the subsequent cohort. The next planned dose level may be reduced, a dose level may be re-tested, or an intermediate dose level selected, based on the emerging data.

The dose level will not exceed 20 mg LSF oral solution (1 mg/mL) per day.

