7.10. Blinding and procedures for unblinding

The study drug and matching placebo will be identical in appearance in order to preserve the single blind with respect to the subject; the subjects are blinded and will not know which treatment (active or placebo) they are given. The Investigator (including clinical, statistics and data management personnel) and the Sponsor (including the study monitor) will remain blinded during each cohort, so as not to potentially introduce bias, unless safety concerns necessitate unblinding (if the knowledge of the treatment administered is useful for the best medical care of an AE). Investigator pharmacy staff, who'll dispense the IMP, will not be blinded at any time.

For safety and dose escalation purposes, the data may be unblinded at the end of each cohort for review by the SRG. Optionally, a separate, unblinded monitor may be used to check drug accountability monitoring during the conduct of the study, following procedures to avoid unblinding other study personnel.

A sealed copy of the randomisation code will be kept in a locked file in the HMR Pharmacy. A copy will also be kept by the Sponsor. The Investigator will be supplied with sealed envelopes, each one containing the treatment allocation for the subject whose number appears on the outside of the envelope. Those envelopes will be kept in the trial master file, readily accessible to clinical staff. Emergency procedures for revealing medication codes are specified later in this section.

If required, as described in Section 11, advisor(s) independent from the study team may be appointed to review unblinded data to assist decision-making during Safety Review Meetings.

When the database is locked at the end of cohorts 1 and 2 and again at the end of cohort 3, the HMR statistician will inform the Sponsor of his or her intention to break the randomisation code for the finished cohorts. The statistician will break the code, and do the statistical analysis of those data.

If unblinding is required in the interest of the safety of a subject, an Investigator will discuss the matter with the Sponsor before opening the individual code-break envelope for that subject. In a medical emergency, the Principal Investigator or delegate may open the individual code-break envelope for that subject without prior consultation with the Sponsor. In that event, the principal Investigator or delegate will

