10.8. Pharmacodynamic Analysis

Pharmacodynamic variables at each planned assessment, and change in pharmacodynamic variables from baseline at each planned post baseline assessment, will be summarised by actual treatment.

11. Safety Review Meetings

Safety will be reviewed throughout the study in Safety Review Meetings. Participants in the Safety Review Meeting ('the Safety Review Group') will be at a minimum the Principal Investigator (or his/her deputy), and at least one medically-qualified Sponsor representative. Optionally, independent advisor(s) may be appointed to advise on dose escalation decisions, if required. Those meetings will follow DNDi SOP CL 26 (Safety Data Review during Phase I clinical trial) and will be described in the Safety Review Group charter.

12. Quality Assurance and Quality Control Procedures

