7.1 Interim Analyses

Interim analyses will be performed. Blinded PK, safety and tolerability data will be reviewed after each cohort for dose selection. Details are given in the Interim Review Plan and in the safety Review Group Charter signed at the beginning of the study.

An additional interim analysis (including interim database lock) will be performed after Cohorts 1 and 2 have completed and unblinded, to evaluate the progression into later phase studies.

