13.2 Protocol Deviations

Before closing the database, data listings will be reviewed to identify any significant deviations and determine whether the data should be excluded from any analysis populations.

Major protocol deviations include subjects who:

- Entered the study even though they did not satisfy the entry criteria.
- Met the criteria for withdrawal from the study but were not withdrawn.
- Received the wrong treatment or incorrect dose.
- Received an excluded concomitant therapy.
- Received investigational product(s) past the expiration date.
- Had their treatment assignment unblinded.

In addition, subjects with minor time deviations (measurements taken outside the allowable windows) will be identified. Allowable time windows for pharmacokinetic samples and other procedures are given in section 8.4 of the study protocol.

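### The Protocol lets the Investigator, who assigns AE causality, see unblinded data at a safety review that the SAP calls blinded, and no supplied text fixes causality first

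*Protocol*

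**What the plan says.** **Permission to unblind.** The Protocol Summary (Trial Design) says that "the Investigator and Sponsor may choose to review unblinded data at the Safety Review Group for a particular cohort" and refers to the Safety Review Group (SRG) Charter for the process. Protocol 7.10 keeps the Investigator and Sponsor blinded while a cohort runs, then adds: "For safety and dose escalation purposes, the data may be unblinded at the end of each cohort for review by the SRG". It does not tie the end of a cohort to a study day.

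**Timing.** Protocol 7.5 lets escalation go ahead once the SRG has reviewed "safety, tolerability and PK data until 48 h after the final dose of study medication in at least 4 subjects on active treatment", which means at least 6 subjects overall. AE reporting ends at the Day 120 visit (Protocol 8.6.4).

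**People.** Under Protocol 11 the SRG consists at minimum of the Principal Investigator or deputy and "at least one medically-qualified Sponsor representative". Independent advisors are optional. Causality is the Investigator's judgement (Protocol 8.6.7), and the drug-related TEAE table uses the Investigator's record (SAP 14.2). The Sponsor determines expectedness (Protocol 8.6.5).

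**SAP.** Section 7.1 says of the per-cohort review: "Blinded PK, safety and tolerability data will be reviewed after each cohort for dose selection". Section 7.2 places unblinding after database lock. Section 13.2 includes among major deviations subjects who "Had their treatment assignment unblinded".

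**The concern.** Two problems are linked. First, the Protocol allows an unblinded SRG review, while the SAP describes a blinded one and treats an opened assignment as a major deviation. A team following one document would breach the other.

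Second, the person who judges whether an event is related to emodepside may learn the allocation while events are still being collected and before the database is locked. With the allocation known, a new event on active treatment is more easily called related and one on placebo less easily, and earlier calls can be revised. AEs are the primary safety endpoint in Protocol 2.2.1. Relatedness also drives the trial stopping criteria in Protocol 7.6.2, which feed the dose escalation criteria in 7.6.1. With so few placebo subjects, a single changed call is visible in the table.

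**Working it through.** The plan gives no figure of its own here, so there is nothing to reproduce. The inputs come from the Schedule of Events, Protocol 7.5 and Protocol 8.6.4.

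**Earliest data cut.** The final dose is on Day 9, and 48 h later is Day 11, as footnote 12 of the Schedule of Events labels it.

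**Calendar time remaining.** (120 − 11)/120 = 109/120 = 90.8%. With the ±2-day window on the last visit:
- Day 118: (118 − 11)/118 = 90.7%
- Day 122: (122 − 11)/122 = 91.0%

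Day 11 is the earliest cut, not a stated meeting date. If the code were opened later (assumed dates):
- Day 14: 106/120 = 88%
- Day 30: 90/120 = 75%

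**Scheduled AE checks remaining** (footnote 11, counted after the first dose):

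| Period | Checks |
|---|---|
| Day 0, 1 to 12 h | 7 |
| Days 1–8, pre-dose | 8 |
| Day 9, pre-dose and 0.5 to 12 h | 9 |
| 24, 36 and 48 h | 3 |
| **Up to 48 h** | **27** |
| 72, 96 and 120 h | 3 |
| Days 17, 20, 23, 27 | 4 |
| Day 30 | 1 |
| Days 60, 90, 120 | 3 |
| **After 48 h** | **11** |

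11/(27 + 11) = 11/38 = 29%. No dosing days remain.

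**Weight of one changed call.** Each cohort has 2 placebo subjects, so one subject is 1/2 = 50 percentage points within a cohort. SAP 7.2 and 18.1 report Cohorts 1 and 2 together, and SAP 11.1 labels placebo by OD or BID. If the OD placebo subjects of those two cohorts are pooled, one subject is 1/4 = 25 points.

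**Which tables are exposed.** Total TEAE counts do not use causality; the drug-related table does. Protocol 10.6.5 counts any event after first dosing as treatment-emergent, so late events enter that table. SAP 14.2 speaks of events emerging during treatment. Read literally, that could leave out new events after Day 11, and the exposure in the table would then be mainly revision of earlier calls.

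**Can the review be blinded as described?** Protocol 10.1 puts PK parameters, glucose and insulin into each review without saying whether they are shown by subject or by group. Subject-level emodepside concentrations would reveal who is on active treatment. Insulin could also give a clue: in the earlier single-dose study, under fasting, "a dose and plasma concentration-dependent decrease in insulin plasma concentration (13 pmol/L or below) after emodepside administration was reported". No masking step is described in the supplied text.

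**The case against.** The best defence is that this is a declared design choice. The trial is openly single-blind with respect to subjects, SRG unblinding is optional, and independent advisors may review unblinded data. Protocol 10 allows the SAP to modify the analysis plans. The process is assigned to the SRG Charter and the Interim Review Plan, which were not supplied and may already require causality sign-off or masked PK.

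Part of this stands: the absence of a safeguard can be asserted only for the supplied text. But the Protocol says staff blinding is there to avoid bias, so the single-blind label does not settle the matter. Nor can an unseen charter remove a conflict between the Protocol and SAP 7.1, 7.2 and 13.2. The SAP's introduction says substantial differences in statistical methods will be identified, and the supplied text identifies none here.

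A reader might also infer more than the documents support:
- **That the Sponsor judges causality.** It determines expectedness; causality is the Investigator's.
- **That a review is fixed for Day 11.** Day 11 is only the earliest data cut.
- **That 91% of the AE information is still to come.** That figure is calendar time. In Part 1 of the earlier study all treatment-related TEAEs resolved within 24 h, and in its Cohort 10 most related eye events began close to Tmax. The terminal half-life of 523 h (523/24 = about 22 days) keeps late events possible, but no document gives their share.
- **That the SRG will see subject-level PK and insulin.** The level of display is not stated.
- **That an SRG unblinding would remove a cohort from analysis.** SAP 13.2 only prompts a review of exclusions, and the Safety Population is everyone dosed. Calling a permitted act a major deviation is still a conflict to resolve.

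**Conclusion.** The point holds in limited form. The Protocol allows the sole assessor of causality to see allocation on a data cut as early as Day 11, the SAP describes the same review as blinded, and nothing supplied fixes causality beforehand. At that cut 91% of calendar time from first dose remains, but 29% of scheduled post-dose AE checks and no dosing. One changed placebo call moves the drug-related rate by 50 points within a cohort, or 25 points if OD placebo is pooled.

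The exposure is confined to the drug-related TEAE table and causality-based stopping decisions. The conclusion assumes that the SRG uses its option to unblind, that whoever attends also assesses causality afterwards or can revise earlier calls before lock, and that the unseen charter has no equivalent safeguard. The document conflict rests on none of these. It should be fixed, although the likely size of any bias cannot be estimated from the documents.

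**What to change.** 1. Reconcile SAP 7.1, 7.2 and 13.2 with the Protocol Summary and Protocol 7.10. State whether SRG review is blinded or optionally unblinded, and exempt Protocol-permitted SRG unblinding from the major-deviation list.
2. If the SRG may unblind, have the Investigator sign off the causality of all AEs to date first. Leave severity and seriousness open to update for ongoing events, because Protocol 8.6.3 records the maximum severity reached and 8.6.5 requires SAE follow-up reports.
3. Record the unblinding date, and flag in Listing 16.2.7.1 any causality assigned or changed after it.
4. Where the review is blinded, show PK, glucose and insulin by group or under scrambled identifiers.
5. Where practical, let whichever of the Principal Investigator and deputy did not attend the unblinded session assess later causality. Protocol 11 already allows either to attend.

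The cost is wording in the two documents and the charter, a short AE sign-off before each unblinded SRG, and one listing flag. Masked packs also need a preparer who does not assess AEs; the independent statistician who prepares the randomisation schedule (Protocol 6) is one candidate.
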